2.1.7 Compliance

Compliance is defined as (duration of treatment/expected duration of treatment). Calculation of duration of treatment is described in [Section 2.4.8](#) and [Section 2.4.9](#).

The expected duration of treatment is calculated as following:

- For non-flare-up treatment, expected duration of treatment is calculated as (last non-flare-up dose date – first non-flare-up dose date) – (sum of (all flare-up cycle dosing periods) + 1).
- For flare-up treatment, expected duration of treatment is calculated as total of expected flare-up cycle dosing periods across all flare-up cycles. Each expected flare-up cycle dosing period is defined as (last flare-up cycle dose date – first flare-up cycle dose date + 1).

Compliance will be summarized for the Principal FAS with descriptive statistics. Compliance in category (<80%, ≥80%) will also be summarized for counts and percentages of subjects.

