## 6.7 Assessment of Subject Compliance

Compliance will be based on the amount of study drug dispensed to the subject and returned to the site.

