The total blood volume drawn from a subject over the course of the entire study (48 months) will range from approximately 66 mL (in the case of no flare-ups) to 182 mL (in the case of two expected flare-ups treated per year, or a total of eight flare-ups treated during the entire study). In the event that the total drawn blood volume exceeds the limits established by the clinical site for pediatric subjects, then priority will be given to the key safety laboratory tests, as outlined in the clinical safety laboratory manual. This will ensure that the total blood volume drawn is within the established limits.

The Investigator will be provided all laboratory results and will review and assess out-of-range findings for clinical significance. Any post-baseline abnormal laboratory value assessed as clinically significant will be recorded as an AE. It is recognized that performing phlebotomy in subjects with FOP is very challenging due to their multiple ankyloses and the potential to cause injury resulting in a flare-up following multiple attempts. The Investigator will be notified about any protocol-specified safety laboratory test that could not be obtained despite at least two attempts. Should this occur, or for those samples that were drawn but were not usable (eg, quantity not sufficient, clotted, sample lost, etc.), the Investigator will assess the subject's condition and determine whether repeated attempts should be made to obtain the missing

laboratory data for that time point, or reassessed at the next scheduled time point based on the subject’s current clinical status (eg, AEs, vital signs) and previous laboratory measures.

Table 5 presents the clinical laboratory parameters that will be assessed in this study.

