### 8.4 Analysis Populations

In Part A, the MOVE subjects will be grouped into the following populations for analysis:

- The Principal Enrolled Population (Principal EP) includes all subjects with the R206H ACVR1 mutation who have not previously been treated with palovarotene and who sign the informed consent form and meet all eligibility criteria of the MOVE Trial.
- The Principal Full Analysis Set (Principal FAS) includes all enrolled subjects in the Principal EP who have a baseline HO volume measurement and at least one post-baseline HO volume measurement in the MOVE trial. For efficacy comparisons to the NHS, the Principal FAS will also include subjects enrolled in the NHS with available baseline and at least one post-baseline HO volume measurements.
- The Principal Per-Protocol Set (Principal PPS) is a subset of the Principal FAS including subjects with no major protocol deviations that are expected to interfere with assessments of the primary endpoint, and with at least 80% compliance to the study drug regimen, over the first 24 months of participation in the study. For efficacy comparisons to the NHS, the Principal PPS will also include subjects in the NHS with available baseline and

at least one post-baseline HO volume measurements and with no major protocol deviations over 24 months that are expected to interfere with assessments of the primary endpoint.

- The Principal Safety Set (Principal SS): includes all enrolled subjects receiving at least one dose of palovarotene in the current study. For safety comparisons to the NHS, the Principal SS will also include subjects enrolled in the NHS with available post-baseline follow-up.
- The Principal Pharmacokinetic Set (Principal PS) includes all enrolled subjects receiving at least one dose of palovarotene and providing evaluable pharmacokinetics data in the current study.

Subjects who do not have the R206H ACVR1 mutation or who have received previous treatment with palovarotene will comprise the Supplementary EP, the Supplementary FAS, the Supplementary PPS, the Supplementary SS, and the Supplementary PS, with these populations defined analogously as above for the subjects with the R206H ACVR1 mutation.

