2.4.8 Duration of Flare-up Treatment

For subjects receiving flare-up treatment, duration of flare-up treatment (days) is defined as total flare-up cycle dosing periods (days) across all flare-up cycles.

For a flare-up cycle, the flare-up cycle dosing period (days) is defined as days that subjects received flare-up-based treatment and is calculated as (last dose date of the flare-up cycle – first date of the flare-up cycle – days where flare-up medications were not taken/interrupted during the flare-up cycle + 1).

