2.4.9 Duration of Non-Flare-up Treatment

Based on the study design, subjects are assumed to be on non-flare-up-based treatment from the date they received the first non-flare-up treatment unless they receive flare-up-based treatment. Thus, duration of non-flare-up treatment (days) will be calculated as (last non-flare-up treatment date - first non-flare-up treatment date – duration of flare-up treatment (days) - days where non-flare-up medications were not taken/interrupted + 1). Duration of flare-up treatment (days) is defined in [Section 2.4.8](#).

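### The SAP's compliance formulas miscount days: full chronic adherence scores above 100%, missed flare-up days are credited as chronic dosing, and the window does not match the protocol's

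*SAP*

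**What the plan says.** SAP 2.1.7 makes compliance a ratio of actual to expected duration of treatment, with separate expected durations for the two kinds of dosing.

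- **Expected flare-up days:** summed over cycles, each counted inclusively as "last flare-up cycle dose date – first flare-up cycle dose date + 1".
- **Expected chronic days:** last minus first chronic dose date, less a bracket containing "sum of (all flare-up cycle dosing periods) + 1".
- **Actual flare-up days (SAP 2.4.8):** the cycle length, counted inclusively, less "days where flare-up medications were not taken/interrupted during the flare-up cycle".
- **Actual chronic days (SAP 2.4.9):** last minus first chronic dose date, less the 2.4.8 flare-up duration, less "days where non-flare-up medications were not taken/interrupted + 1".

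SAP 2.1.7 reports compliance for the Principal FAS, including a split at 80%. SAP 2.3 requires at least 80% compliance for the Principal PPS. It gives no time window, does not cite 2.1.7, and does not say whether the cut applies to chronic, flare-up or pooled compliance.

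The protocol differs on two points. Section 8.4 defines the PPS by subjects "with at least 80% compliance to the study drug regimen, over the first 24 months of participation in the study". Section 6.7 says "Compliance will be based on the amount of study drug dispensed to the subject and returned to the site".

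**The concern.** A compliance ratio should return exactly 100% when every dose is taken and should fall when doses are missed. The chronic ratio does not return 100% under full adherence. A missed flare-up day, which should only lower compliance, also raises the count of chronic days taken. Both effects push the score upward.

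The purpose of the 80% rule is to remove poorly adherent subjects from the PPS. SAP 2.4.4 repeats the Bayesian compound Poisson and wLME analyses in that set, and SAP 2.3 says these PPS analyses belong to the interim CSR that supports the regulatory filings. If compliance reads high, the set can keep subjects whom it is meant to exclude, and the FAS compliance table looks better than the dosing was.

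**Working it through.** The documents state no compliance result to reproduce, so the test is whether the formulas return true day counts.

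**Notation.** F and L are the first and last chronic dose dates. C is total calendar days in flare-up cycles, m is missed flare-up days, and n is missed chronic days. S = C − m is the 2.4.8 duration. D = (L − F + 1) − C is the true number of chronic days. All cycles are taken to lie between F and L.

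**Formulas.**
- Actual chronic days (2.4.9): L − F − S − n + 1 = D + m − n
- Expected chronic days (2.1.7, with S as defined in 2.4.8): L − F − (S + 1) = D + m − 2
- True chronic compliance: (D − n)/D

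With n = 0, actual exceeds expected by two days. The m missed flare-up days enter both numerator and denominator, which pulls the ratio toward 100%.

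**Step 1: the two days.** Assume 24 months = 730 days and no flare-ups.
- Full adherence: 730/728 = 100.3%.
- 147 days missed: 583/728 = 80.08%, a pass; the true value is 583/730 = 79.86%.
- 148 days missed: 582/728 = 79.95%, a fail.

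The correct limit is 146 missed days (584/730 = 80.00%), so the cut moves by one day in 730.

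**Step 2: missed flare-up days.** Protocol 7.2.6 considers a subject "in the case of two expected flare-ups treated per year", and Protocol 3.1 gives an 84-day course. Over 24 months that is 4 × 84 = 336 flare-up days, leaving D = 730 − 336 = 394. The missed days are assumptions: m = 67 and n = 93. Then S = 336 − 67 = 269.

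| Measure | SAP score | True value |
|---|---|---|
| Flare-up | 269/336 = 80.1% | 269/336 = 80.1% |
| Chronic | (729 − 269 − 93 + 1)/(729 − 270) = 368/459 = 80.2% | 301/394 = 76.4% |
| Pooled | (368 + 269)/(459 + 336) = 637/795 = 80.1% | (301 + 269)/730 = 570/730 = 78.1% |

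This subject meets 80% on each component and pooled, and is truly below it on chronic and overall compliance. If 2.1.7 were read as subtracting calendar cycle lengths while 2.4.9 stayed as printed, the chronic score would be 368/(729 − 337) = 368/392 = 93.9%.

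**Step 3: range.** Take 730 days with two 84-day cycles (C = 168, D = 562). The table gives the lowest true chronic compliance that still scores 80% on the chronic ratio.

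| Missed flare-up days | Flare-up compliance | 2.1.7 subtracts net days | 2.1.7 subtracts calendar days |
|---|---|---|---|
| 16 | 90.5% | 79.2% | 76.9% |
| 40 | 76.2% | 78.3% | 72.6% |
| 80 | 52.4% | 76.9% | 65.5% |

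With m = 0 only the two days remain.

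**Step 4: the window.** Both denominators end at the last dose taken. A subject who takes every dose and stops on day 90 scores 90/88 = 102.3%; 90 days is 12.3% of 730. A flare-up course dropped on day 20 scores 20/20 = 100%; 20 days is 23.8% of the planned 84.

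**The case against.** **The bracket is a typing slip.** It is, and alone it is trivial. Section 2.4.9 and the flare-up formula both count inclusively, so the intent is clear. It is still the printed definition.

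**The flare-up ratio would catch such subjects.** Often it would. A reader might infer that anyone with heavy flare-up non-adherence passes the cut. Take 100 of 336 flare-up days and 98 of 394 chronic days missed. The chronic score is 396/492 = 80.5% against a true 296/394 = 75.1%. But the flare-up score is 236/336 = 70.2%, and the pooled score is 632/828 = 76.3%. That subject passes only if the cut is applied to chronic compliance alone, which no section says; the PPS wording refers to the whole regimen. The case in step 2 does not depend on that reading.

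**Expected chronic days are always two short.** A reader might infer this too. Against true days it holds only when no flare-up dose is missed. In step 2 the expected figure is 459 against a true 394, which is 65 too many.

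**Missed flare-up days could be deducted again as missed chronic days.** The wording of 2.4.9 concerns non-flare-up medication, so this is not the natural reading. If it were programmed that way, step 2 would give 301/459 = 65.6%, which is wrong in the other direction.

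**Stopping at the last dose is a legitimate choice.** Adherence while on drug differs from persistence, and the SAP reports discontinuations separately (2.2, 2.4.3). Protocol 8.4 names a period but no 730-day denominator, the dispensed/returned basis gives no denominator either, and Protocol 6.5 allows dosing to stop. The documents therefore do not show that early stoppers are wrongly kept. What stands is that the SAP drops the protocol's window and basis, and SAP 1.9, which lists changes to the protocol's statistical section, mentions neither.

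**The consequence is small.** This is correct: the primary analysis uses the FAS, and no PPS analyses are planned after the interim CSR.

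**Conclusion.** Wrong as written. The misplaced 1 makes actual chronic days exceed expected by two when no chronic dose is missed, which is worth about one day in 730 at the cut. Subtracting flare-up days net of missed doses credits those doses as chronic treatment and biases chronic compliance upward. In the illustration it reads 80.2% against a true 76.4%, and 80.1% pooled against 78.1% overall.

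The size rests on assumed missed-dose counts, on a flare-up load that Protocol 7.2.6 uses as the upper end of a range starting at no flare-ups, and on missed flare-up days not being deducted twice. The link from 2.1.7 to the PPS cut is an inference from the shared 80% threshold and the absence of any other compliance definition in the SAP. How many subjects change status cannot be known from the documents.

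The last-dose endpoint is a mismatch with the protocol to be reconciled, not a proven error. A reader might infer that the main efficacy result is affected; it is not. The reach is the supportive PPS analyses and the FAS compliance table.

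**What to change.** 1. In 2.1.7, set expected chronic days to (last − first + 1) minus the sum over cycles of (last − first + 1). Subtract the same calendar cycle lengths in 2.4.9, counting only cycle days that fall between the first and last chronic dose. Full adherence then gives exactly 100%, and the step 2 case gives 301/394 = 76.4% chronic and 570/730 = 78.1% pooled.
2. In 2.3, state that the PPS cut uses this measure, and whether 80% must be met on each component or pooled.
3. Reconcile the window and basis with Protocol 6.7 and 8.4. End the window at Month 24, or at the subject's December 2019 or January 2020 dosing cut-off if earlier. A flat 24-month denominator would mark subjects non-compliant because of the clinical hold or the January 2020 interruption.
4. Check what was programmed, and report whether PPS membership in the interim CSR changes. SAP 3.3 does not plan to rerun those analyses, so this will not happen by default.

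The cost is a few lines of SAP text and a re-derivation from existing dosing records. The PPS analyses need repeating only if membership changes.

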2.2 Disposition of Subjects

This section describes the disposition for treatment status, subject status and the patient populations.

Screened subjects are defined as all subjects who sign the informed consent.

Enrolled subjects include all subjects who sign the informed consent and meet all eligibility criteria of the MOVE Trial.

For subjects in the MOVE Trial, the total number of subjects for each of the following categories will be presented in a table:

- Screened subjects
- Screen failure subjects and the reasons for screen failure
- Enrolled subjects
- Enrolled and treated subjects including by whether the subjects crossed over from the NHS
- Subjects who permanently discontinued study drug by reason for discontinuing study drug;
- Subjects who completed the MOVE Trial
- Subjects who discontinued the MOVE Trial by reason for discontinuing study

For all categories of subjects (except for the screened category), percentages will be calculated using the number of enrolled subjects as the denominator. Reasons for study drug discontinuation will be presented in tables giving numbers and percentages. The NHS subject disposition will be summarized using the categories above, where applicable.

All critical or major deviations potentially impacting efficacy analyses and other major/critical deviations will be summarized in tables giving numbers and percentages of deviations by treatment group.

Additionally, the analysis populations will be summarized in a table by subject counts based on the enrolled populations (see definitions in [Section 2.3](#)).

2.3 Analysis Populations

The MOVE Trial subjects will be grouped into the following populations for analysis:

- The Principal Enrolled Population (Principal EP) includes all subjects with the R206H ACVR1 mutation who have not previously been treated with palovarotene and who sign the informed consent form and meet all eligibility criteria of the MOVE Trial. For the NHS, the Principal Enrolled Population will include all subjects enrolled.
- The Principal Full Analysis Set (Principal FAS) includes all enrolled subjects in the Principal EP who have a baseline HO volume measurement and at least one post-baseline HO volume measurement in the MOVE trial. For efficacy comparisons to the NHS, the Principal FAS will also include subjects enrolled in the NHS with available baseline and at least one post-baseline HO volume measurement.
- The Principal Per-Protocol Set (Principal PPS) is a subset of the Principal FAS including subjects with no major protocol deviations that are expected to interfere with assessments of the primary endpoint, and with at least 80% compliance to the study drug regimen. For efficacy comparisons to the NHS, the Principal PPS will also include subjects in the NHS with available baseline and at least one post-baseline HO volume measurement and with no major protocol deviation that are expected to interfere with assessments of the primary endpoint. Note that no analyses using the Principal PPS are planned after the interim CSR used to support the global regulatory filings.
- The Principal Safety Set (Principal SS) includes all enrolled subjects with the R206H ACVR1 mutation receiving at least one dose of palovarotene in the current study. For safety comparisons to the NHS, the Principal SS will also include subjects enrolled in the NHS with available post-baseline follow-up.
- The Principal Pharmacokinetic Set (Principal PS) includes all enrolled subjects with the R206H ACVR1 mutation receiving at least one dose of palovarotene and providing evaluable pharmacokinetic data in the current study.
- Principal Restart Full Analysis Set (Principal RFAS) includes all enrolled subjects in the Principal EP who restarted palovarotene therapy after January 2020 and have at least two assessments on or after restart e.g. 2 WBCT scans for HO volume measurements in the MOVE trial. Analyses involving this population will primarily be descriptive and will include records after palovarotene restart.

- Part C Analysis Set includes all skeletally immature subjects who stopped taking study medication for any reason before completion of Part A/B and had at least one follow-up visit following last dose. All analyses involving this population will be descriptive.

Subjects who do not have the R206H ACVR1 mutation or who have received previous treatment with palovarotene will comprise the Supplementary EP, the Supplementary FAS, the Supplementary SS, the Supplementary PS, and the Supplementary RFAS, with these populations defined analogously as above for the subjects with the R206H ACVR1 mutation. (Due to the limited sample size, there is no Supplementary PPS.) The Principal populations will be used for all analyses described in this SAP. The Supplementary populations will be supportive and summarized separately and, unless otherwise specified, will not be used in hypothesis testing.

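### As worded, the SAP's Principal Safety and PK Sets overlap the Supplementary sets: a dosed R206H subject previously treated in Phase 2 meets both definitions

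*SAP*

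**What the plan says.** SAP 2.3 builds most Principal populations from one base. The Principal EP "includes all subjects with the R206H ACVR1 mutation who have not previously been treated with palovarotene" and who consented and met the eligibility criteria. The FAS "includes all enrolled subjects in the Principal EP who have a baseline HO volume measurement" and a later one. The Restart FAS "includes all enrolled subjects in the Principal EP who restarted palovarotene therapy after January 2020" and have enough later assessments. The PPS is a subset of the FAS. All of these are therefore palovarotene-naive.

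The two remaining sets are defined differently. The Principal SS "includes all enrolled subjects with the R206H ACVR1 mutation receiving at least one dose of palovarotene in the current study". The Principal PS takes enrolled R206H subjects "receiving at least one dose of palovarotene and providing evaluable pharmacokinetic data in the current study". Neither refers to the Principal EP. SAP 2.2 gives enrolment no naive condition: "Enrolled subjects include all subjects who sign the informed consent and meet all eligibility criteria of the MOVE Trial".

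The Supplementary sets follow: "Subjects who do not have the R206H ACVR1 mutation or who have received previous treatment with palovarotene will comprise the Supplementary EP" and the matching FAS, SS, PS and RFAS. SAP 2.3 adds that the Supplementary populations are reported apart from the Principal ones. Protocol 8.5.3 likewise says safety analyses use the Principal SS and, separately, the Supplementary SS.

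**The concern.** A Phase 2 participant with R206H who received palovarotene there, and is dosed in MOVE, meets the SS and PS definitions on both sides. The text then describes two overlapping sets where both documents describe two separate ones. The Principal SS as worded is neither all-treated (it leaves out other mutations) nor naive-only (it keeps previous Phase 2 exposure).

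Three things depend on this. SAP 2.4.5 runs all safety analyses on these sets, and SAP 2.4.7 runs the PK analyses on both PSs. The Principal SS is also the set compared with the natural history study (NHS), whose subjects had no previous palovarotene (Protocol 8.1).

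The safety rules also fit some of these subjects poorly. Protocol Table 1 (footnote on the WBCT scan) and Protocol 7.4.1 provide for Phase 2 subjects who are already on chronic treatment when they enter. SAP 2.4.5 takes baseline as the last value before the first chronic dose of study drug, and does not count an abnormality present at baseline as new-onset. If the first MOVE dose is meant, baseline for such a subject is on-drug, and a laboratory or ECG abnormality that arose in Phase 2 and persists would not be counted.

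**Working it through.** **Set logic**

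- Principal SS (SAP) = R206H and dosed.
- Supplementary SS = (not R206H, or previously treated) and dosed.
- Intersection = R206H and previously treated and dosed.

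The PS gives the same result with evaluable PK data added to each line. Protocol 5.1.1 admits participants from PVO-1A-202 and PVO-1A-204, so the intersection can contain subjects. No rule in either document removes them from one side.

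**Counts**

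Protocol 3.1 plans up to 99 naive R206H subjects and up to 11 with other mutations or previous Phase 2 participation, with a maximum of 110. Check: 99 + 11 = 110, which agrees. SAP 2.4.4 also reports 99 naive R206H subjects enrolled.

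Let x be the number of previously treated R206H subjects who are dosed. The documents do not give x. The 11 places are shared with other mutations, so x is taken over the range 0 to 11, with all enrolled subjects assumed dosed.

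- Literal Principal SS = 99 + x
- Previously treated share = x / (99 + x)
- Principal SS + Supplementary SS = 99 + x + 11 = 110 + x

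| x | Principal SS | Share previously treated | Sum of the two sets |
|---|---|---|---|
| 0 | 99 | 0% | 110 |
| 1 | 100 | 1/100 = 1.0% | 111 |
| 3 | 102 | 3/102 = 2.9% | 113 |
| 6 | 105 | 6/105 = 5.7% | 116 |
| 11 | 110 | 11/110 = 10.0% | 121 |

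**Effect on an incidence**

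If the recorded rate of an event differs by d between previously treated and naive subjects, the Principal SS incidence moves by d × x / (99 + x). At x = 11 the factor is 0.10, so differences of 10, 20 and 50 percentage points move it by 1, 2 and 5 points. At x = 3 the factor is 0.029, and the same differences move it by 0.3, 0.6 and 1.5 points. The values of d are illustrative.

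**Protocol comparison**

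Protocol 8.4 defines the Principal SS as any enrolled subject who took a dose, without even the R206H limit, and its Principal PS is equally open. Read literally, the whole Supplementary SS lies inside the Principal SS: up to 110 + 11 = 121 memberships for 110 subjects, whatever x is. The SAP added the mutation half of the restriction but not the exposure half.

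**After nesting in the Principal EP**

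The overlap is 0. The Principal SS is at most 99 and the Supplementary SS at most 11, together 110.

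**The case against.** The strongest reply is that this is a drafting slip whose intent is plain. SAP 2.3 says the Supplementary sets are reported apart, and it uses R206H as shorthand for the whole Principal group when it says those sets are defined by analogy. A programmer might well place previously treated subjects only in the Supplementary sets. That is probably the intent, and a reader should not infer that anyone has actually been counted twice. But the definitions do not say so, and someone else working from the literal text would build a different denominator.

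A second reply is that the documents attach the naive restriction to the efficacy analysis (Protocol 3.2 and 8.1), and that an all-treated R206H safety set could be deliberate. It is true that neither document requires the main safety tables to be naive-only. A deliberate choice of that kind would still conflict with assigning the same subjects to the Supplementary SS and promising separate reporting.

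Two stronger readings are tempting and not supported:

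- A reader might infer that Phase 2 subjects were selected because they tolerated earlier exposure. Protocol 5.1.1 gives country of residence and long-distance travel as the reasons, and states no tolerance criterion.
- A reader might object that the safety and efficacy populations then fail to match. They differ by design, since the FAS needs HO volumes and the SS needs one dose. Nesting would not make them identical.

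**Conclusion.** The point holds as a defect of definition. As worded, the Principal and Supplementary SS share members whenever a dosed R206H subject had palovarotene in Phase 2, and the PS do so when such a subject also has evaluable PK data. This contradicts the separation stated in both documents.

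Its size is unknown. At planned maxima it is 0 to 11 subjects. The 10% figure is an upper bound, reached only if all 11 places went to previously treated R206H subjects, and should not be read as the expected dilution.

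The consequence is confined to safety and PK outputs, which are largely descriptive. The primary and secondary efficacy analyses use the Principal FAS, which is nested in the Principal EP, so efficacy inference, alpha and power do not change.

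The on-drug baseline is a possibility for a subset only. It needs a subject who was already on chronic palovarotene at entry, and it needs the SAP baseline to refer to the first MOVE dose. Where both apply, the error is towards too few new-onset abnormalities.

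**What to change.** In SAP 2.3, define the Principal SS as enrolled subjects in the Principal EP who received at least one dose in MOVE, and the Principal PS likewise with evaluable PK data. The FAS and Restart FAS already use this construction. Keep the existing NHS sentence for the safety comparison. Align Protocol 8.4 and the synopsis, because changing the SAP alone would leave the two documents in conflict.

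SAP 3.3 says analyses in the interim CSR are not planned to be rerun for the final CSR. The final CSR should therefore state which rule the interim CSR applied and give the number of subjects who meet both definitions.

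The cost is a few words in each definition and one count, with no new data. Principal SS and PS denominators fall by at most 11 compared with the literal SAP rule. If the literal rule was used in the interim CSR, denominators may differ between the two reports, and the final CSR should explain why.
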